6.3. Analysis Populations and Datasets

Three patient populations are defined for the analyses in this study with detailed information listed in [Table 6.1](#). Analyses datasets specifying data exclusion are listed in [Table 6.2](#).

Unless otherwise specified, listings will include FAS for all randomized patients; safety analyses, except for hypoglycemia events, will be conducted in the mITT population with the FAS; and efficacy analyses including primary and key secondary efficacy analyses will be conducted in the mITT population with the EAS.

Table 6.1. Analysis Populations

Population	Definition
All Entered	All patients who signed informed consent forms (ICFs)
All randomized (Intent-to-Treat [ITT])	All patients who were randomized to a treatment arm
Safety Population (Modified Intent-to-Treat [mITT])	All randomized patients who have taken at least 1 dose of the study medication. This is different from what is stated in the protocol. Analyses using the mITT population will be presented by the planned treatment group.

Table 6.2. Analyses Datasets

Analysis Dataset Name	Description
Full Analysis Set	All data available
Efficacy Analysis Set	Only include data on study medication without using rescue medication, i.e., excluding data after rescue medication initiation or after study treatment discontinuation (last dose date +7).

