HbA1c	X		X			X		X		X	X	X
Fasting glucose	X		X			X		X		X	X	X
Total and active GLP-1/GIP			X			X		X		X	X	
7-point SMBG			X ¹							X ^j		
PK ^k						X		X		X	X	X
Immunogenicity			X			X		X		X	X ¹	X
Nonpharmacogenetic stored samples			X							X		

Abbreviations: AE = adverse event; BG = blood glucose; BP = blood pressure; ECG = electrocardiogram; eGFR = estimated glomerular filtration rate; ET = Early Termination; FSH = follicle-stimulating hormone; GLP-1 = glucagon-like peptide-1; GIP = glucose-dependent insulinotropic peptide; HbA1c = hemoglobin A1c; IWRS = interactive web response system; LH = luteinizing hormone; PK = pharmacokinetics; PR = pulse rate; SMBG = self-monitoring of blood glucose; T = telephone visit; TE = treatment emergent; Term. = termination.

- a Telephone visits occur during the week following a dose escalation and should be done 3 to 6 days after a site visit for dose escalation and administration. At telephone visits, the sites should call the patient, ask how the patient is, and ask whether the patient would like to come to the site for assistance with the next study drug dilution and administration. Sites should also remind patients to write down any AEs in their diaries at the telephone visits (as well as at all site visits).
- b Visit should occur approximately 1 week after the last dose (Dose 12).
- c Additional physical examinations may be performed throughout the study if determined necessary due to patient symptoms.
- d Visit should occur 4 weeks after the last dose of study drug or 3 weeks after Visit 10.
- e ECGs should be collected prior to all blood draws and study drug administrations. Local ECGs will be collected for screening (Visit 1) and Early Termination. Centralized ECGs, collected in supine position and in triplicate, should be collected for all other designated visits.
- f Screening laboratory tests include serum hepatitis B surface Ag, hepatitis C antibody (Ab), and human immunodeficiency virus (HIV) Ab tests for all patients (see Appendix 2).
- g Serum pregnancy test will be performed by central laboratory at Visit 1 for women of child-bearing potential. For the remainder of the study, a urine pregnancy test may be performed at the investigator's discretion if pregnancy is suspected during the study (local laboratory). A urine pregnancy test (local) should be given to all women of child-bearing potential at Visit 3 prior to administration of first dose of study drug to confirm lack of pregnancy.

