8.1.2. Temporary Discontinuation from Study Treatment

After randomization, the investigator may temporarily discontinue study drug, for example, due to an AE (eg, nausea and vomiting), or a clinically significant laboratory value. If study drug discontinuation is due to an AE, the event is to be followed and documented. Every effort should be made by the investigator to maintain patients in the study and to restart study drug promptly after any temporary discontinuation, as soon as it is safe to do so. The dates of study drug discontinuation and restart will be documented. Patient noncompliance should not be recorded as temporary discontinuation of study drug on the eCRF. If ≥ 2 doses of study medication (consecutive or not) are missed for any reason, then the patient should be permanently discontinued from study medication.

In the event that the patient requires the discontinuation of the study drug, he/she may continue participation in the study, attend all visits, and undergo all protocol procedures, and patient data from the time of discontinuation of study drug will not be included in the primary analyses.

After study drug discontinuation, patients may commence any standard diabetes therapy in line with local or regional standards of care, and as considered appropriate by the investigator.

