6.1.1. Analysis of Repeated Measures

The mixed model for repeated measures (MMRM) using restricted maximum likelihood (REML) will be used to fit change from baseline values at all scheduled visits. The model will include the treatment group, strata (that is, baseline HbA1c category, baseline BMI category, and metformin use [yes, no]), visit, and treatment-by-visit interaction as fixed effects, baseline value of the dependent variable as a covariate, and patient as a random effect. If the analysis is on the primary endpoint, baseline HbA1c category will not be included in the model in addition to the continuous covariate of baseline HbA1c. To model the covariance structure within patients, the unstructured covariance matrix will be selected initially. If the unstructured covariance structure leads to nonconvergence, the following covariance structures will be tested in order:

- Toeplitz with heterogeneity
- autoregressive with heterogeneity
- compound symmetry with heterogeneous variances
- Toeplitz
- autoregressive
- compound symmetry without heterogeneous variances
- compound symmetry

The first covariance structure that converges will be used.

Kenward-Roger method will be used to estimate the denominator degrees of freedom and the restricted maximum likelihood approach will be used to determine the model estimates.

The MMRM model will present least squares (LS) mean estimates for each scheduled week by treatment group and 2-sided 95% CIs for mean changes from baseline within and (when warranted) between treatments. T-statistics corresponding to the Type III sums of squares for the differences in the LS means will be used to obtain p-values for treatment group comparisons.

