6.2. Patient Disposition

All patients who discontinue the study will be identified, and the extent of their participation in the study will be reported. If known, a reason for their discontinuation will be given. The primary reasons for discontinuation will be listed and will be summarized by treatment. The percentage of patients discontinuing from each treatment will be compared using the Fisher's exact test.

Patient statuses at the end of the 12-week treatment period will be summarized, displaying the numbers of patients:

- entered
- screen failed, along with the primary reason for screen failure
- randomized
- randomized and not treated
- permanently discontinued from treatment, along with the primary reason for treatment discontinuation
- discontinued from study, along with the primary reason for study discontinuation
- completed 12 weeks blinded treatment
- completed study

The summary of status at the end of the 12-week treatment period will count patients by randomized treatment group and overall, except that “Entered” and “Screen failures” only apply to the overall entered population. Entered is defined as signing an informed consent form (ICF). The percentage of patients discontinuing from each treatment will be compared using the Fisher’s exact test.

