6.5. Treatment Compliance

Treatment compliance will be listed using all randomized patients and summarized using the mITT population using the FAS for the listings and summaries. For a given patient, overall compliance for treatment period is defined as not missing 2 or more doses of the assigned treatment in the study. Patients who miss 2 or more doses at any point during the study will be considered significantly noncompliant.

The number and percent of patients compliant during the 12-week treatment period will be summarized at Week 12 using the safety population by the actual treatment group.

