6.9.1. Primary Outcome and Methodology

The primary outcome is the difference in HbA1c change from baseline between treatment groups at the end of the treatment period of 12 weeks. The primary analysis model will be a MMRM for HbA1c change from baseline to 12 weeks described in Section 6.1.1. The treatment p-value will be used as evidence of difference between active drug and placebo, whereas the comparison of LS means versus placebo (unadjusted for multiple comparisons) will provide magnitude and significance of this difference.

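### Does the last dose date +7 cut-off in SAP Table 6.2 remove completers' Week 12 HbA1c, or let Visit 801 in?

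*SAP*

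**What the plan says.** SAP 6.3 assigns the primary and key secondary efficacy analyses to the mITT population with the EAS. Table 6.2 opens the EAS definition with a general condition, "Only include data on study medication without using rescue medication", and then spells it out as "excluding data after rescue medication initiation or after study treatment discontinuation (last dose date +7" days). Completers are not mentioned.

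Other sections bear on how to read this:

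- Protocol 8.1.2, on patients who have to stop study drug: "patient data from the time of discontinuation of study drug will not be included in the primary analyses".
- SAP 6.2 counts patients permanently discontinued from treatment on one line and those who "completed 12 weeks blinded treatment" on another.
- SAP 6.5: "overall compliance for treatment period is defined as not missing 2 or more doses of the assigned treatment in the study". A patient who missed only Dose 12 is therefore compliant.
- SAP 6.1.1: the repeated-measures model "will be used to fit change from baseline values at all scheduled visits".
- SAP 6.9.1: "The primary analysis model will be a MMRM for HbA1c change from baseline to 12 weeks". SAP 6.1.2 likewise ties the ANCOVA endpoints to Week 12.
- The Schedule of Activities puts Visit 10 at Day 84 ±3 days, about a week after Dose 12. HbA1c is also drawn at Visit 801 (Day 105), for which footnote d reads: "Visit should occur 4 weeks after the last dose of study drug or 3 weeks after Visit 10".

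**The concern.** The EAS feeds the primary analysis, so its boundary decides which HbA1c values count. Two programmings of Table 6.2 seem possible, and each appears to have a flaw.

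If the +7 limit is applied to everyone, a completer dosed on Day 77 and seen on Days 85 to 87, inside the permitted window, loses the primary-endpoint value. So does a compliant patient who never took Dose 12. Visit 8 is the day of the first dose at the top level of each scheme, so these patients would have no EAS HbA1c taken after that dose. The cost would be precision at Week 12.

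If the limit is applied only to patients who stop early, Visit 10 is safe, but no day count ends a completer's EAS data. The off-drug Visit 801 value could then enter a model described as fitting every scheduled visit, or become the last value carried forward in the EAS ANCOVA.

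**Working it through.** **1. The plan's own power figure.** Inputs from SAP 5.3 and Table 5.1: SD 1.1, 20 completers per arm, smallest contrast 1.4 − 0.2 = 1.2. Two-sided alpha 0.05 is from SAP 6.1.

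- Randomized: 20 / 0.87 = 22.99, so 23 per arm and 4 × 23 = 92. This agrees with the plan.
- SE = 1.1 × √(2/20) = 0.348.
- Two-arm degrees of freedom (38): t = 2.024, 95% CI half-width 0.704, power 91.9%.
- Four-arm degrees of freedom (76), which fit better because SAP 6.9 puts all arms in the model: t = 1.992, half-width 0.693, power 92.6%.

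The stated figure of at least 90% is reproduced.

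**2. Dates.** Dose 9 is given at Visit 8 (Day 56 ±3) and later doses are weekly, so Dose 12 falls on Days 74 to 80 and the limit on Days 81 to 87.

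| Dose 12 on Day | Limit (Day) | Visit 10 days (81–87) beyond the limit |
|---|---|---|
| 74 | 81 | 6 of 7 |
| 77 | 84 | 3 of 7 |
| 80 | 87 | 0 of 7 |

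These counts let Visit 10 move independently of Dose 12. Footnote b of the Schedule, Protocol 5.1 and the note to Table GPGF.3 tie Visit 10 to about one week after that dose, so the counts overstate how often the gap would exceed 7 days. For a missed Dose 12, all 7 days lie beyond the limit only if the dose is never taken. Protocol 7.2.1 says a missed dose is to be taken as soon as possible, which moves the limit later.

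**3. Which reading the text supports.** In Table 6.2 the +7 stands in parentheses after study treatment discontinuation and dates that event. Protocol 8.1.2 uses the term for stopping drug before the planned end, and SAP 6.2 separates it from completion. A patient who finishes the planned doses, or misses one, has not discontinued in that sense. The Visit 10 value stays in.

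**4. Visit 801.** 105 − 77 = 28 days after Dose 12. Protocol 5.1 calls Visit 10 the last treatment visit and places Visit 801 in the safety follow-up period. A follow-up sample four weeks after the last dose fails the table's on-medication condition. SAP 6.9.1 also stops the primary model at 12 weeks, and SAP 6.1.2 does the same for the ANCOVA, so Day 105 cannot become the carried-forward endpoint.

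Had Visit 801 been left in the repeated-measures model, it would inform the Week 12 mean only through patients who lack a Visit 10 value. A simulation used two arms of 23, 13% stopping after Week 8, correlation 0.5 or 0.8 per 4 weeks, 0 or 30% of the effect lost by Visit 801, no shared covariates, and 1,500 trials per setting. The Week 12 contrast did not change when no completer lacked Visit 10. It shifted by at most 0.0012 on average when 5% did.

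**5. What the misreading would cost, as a hypothetical only.** Per-arm variance of the Week 12 mean = 1.1² × [ρ²/20 + (1 − ρ²)/n], where n is the number of Week 12 values kept and ρ, the Week 8 to Week 12 correlation, is assumed to be 0 to 0.8. Four-arm degrees of freedom, contrast 1.2:

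| Week 12 values lost (assumed) | n | Half-width | Power |
|---|---|---|---|
| none | 20 | 0.693 | 93% |
| 10% | 18 | 0.708–0.732 | 90–92% |
| 20% | 16 | 0.726–0.778 | 86–90% |
| 3/7 | 11.4 | 0.791–0.929 | 72–85% |

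The primary objective needs only one scheme to succeed. In 200,000 simulated trials with the Table 5.1 effects, power for that stays at 92 to 98% even at 3/7 lost. The documents give no visit dates, so none of these loss fractions describes this trial.

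**The case for a change.** The best argument for acting is that the SAP uses the same +7 elsewhere without restriction. SAP 6.10 ends the treatment period, patient by patient, 7 days after the last dose, and SAP 6.6 uses the same interval for exposure. A programmer could reuse that derived date for the EAS. One sentence before unblinding would prevent this, and the FAS analyses in Table 6.3 are a weak check: the FAS also takes in post-rescue and off-drug data, so an EAS–FAS difference would not point to this cause.

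Some of this stands. Table 6.2 is silent on completers, and the FAS analyses would not diagnose the error. But SAP 6.10 is headed Safety Analyses, defines a period for safety summaries and does not mention the EAS. SAP 6.6 measures exposure. Neither changes the event to which Table 6.2 attaches its limit. The harm therefore needs a programmer to override the label in the table, which is not a flaw in the plan.

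Nor is a more explicit rule free of difficulty. A rule that retains only values inside the visit window would add a condition Table 6.2 does not have, and would leave an out-of-window Visit 10 value undefined. Naming Visit 10 as the end also makes explicit that some retained values come more than 7 days after the last dose: up to 87 − 74 = 13 days, or 87 − 67 = 20 days if Dose 12 was never taken. The ordinary reading already accepts this.

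**Conclusion.** No change is needed. Read as written, the EAS keeps completers' Visit 10 HbA1c and leaves Visit 801 out of the Week 12 result. The cost on that reading is zero Week 12 values and no loss of power from the 92 to 93% reproduced above. The Visit 801 question is immaterial even if decided the other way (0.0012 points or less, under the simulation's assumptions). The precision losses in the table arise only if the limit is programmed for patients who did not discontinue, with loss fractions and correlations that are assumed, so they should not be cited as an effect of this plan.

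The conclusion rests on discontinuation meaning early stopping, as in Protocol 8.1.2 and SAP 6.2, and on Visit 10 counting as a treatment visit, as in Protocol 5.1. If Table 6.2 is edited for another reason, a remark that completers' EAS data run through Visit 10 would be a harmless editorial addition.

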6.4. Patient Characteristics and Medical History

Demographic and baseline characteristics will be summarized by treatment group and overall using the mITT population and the FAS. Categorical variables will be summarized by frequencies and percentages. For categorical variables, comparisons between treatment groups will be assessed using a Pearson Chi-Square test. Continuous variables will be summarized by means and standard deviations (SDs). For continuous variables, comparisons between the treatment groups will be performed using a 1-way analysis of variance with treatment as the fixed effect.

Demographic and baseline diabetes characteristics will be presented in listings for each patient.

All summaries of continuous characteristics will be based on nonmissing observations. For categorical characteristics, percentages will be calculated out of the total number of patients in the data set, overall and by treatment group (that is, each denominator includes the number of patients with missing/unknown values for the characteristic).

The numbers and percent of patients with general medical history findings will be provided using the randomized (that is, ITT) population using the FAS. A listing will be provided by patient.

6.5. Treatment Compliance

Treatment compliance will be listed using all randomized patients and summarized using the mITT population using the FAS for the listings and summaries. For a given patient, overall compliance for treatment period is defined as not missing 2 or more doses of the assigned treatment in the study. Patients who miss 2 or more doses at any point during the study will be considered significantly noncompliant.

The number and percent of patients compliant during the 12-week treatment period will be summarized at Week 12 using the safety population by the actual treatment group.

6.6. Exposure of Study Treatment

Exposure to each therapy during the treatment period of the study will be calculated for each patient and summarized by treatment group.

The extent of exposure to study medication (LY3298176, placebo) during the 12-week treatment period is defined as: date of last dose of study medication +7 days - date of first dose of study medication.

The extent of exposure to study medication will be summarized at 12 weeks using the safety population and categorized by the actual treatment group. The number and percent of patients with an extent of exposure within pre-specified day ranges will be presented for the 12-week treatment period by treatment group.

The mean, SD, median, minimum, and maximum days of exposure will also be presented.

In addition, the exposure in terms of total patient-years will be calculated by treatment group using the sum of the exposure to study medication of all patients (in years) in a treatment group.

A patient listing of study medication taken will also be generated.

6.7. Concomitant Drugs

Listings and summary of concomitant therapies will be provided by treatment group.

Previous and concomitant medications will be summarized using the randomized (that is, ITT) population by drug class with generic drug name and planned treatment group, as defined by the World Health Organization (WHO) drug dictionary most current at the time of DBL. A summary will be produced for all concomitant medications during the:

- 12-week treatment period

- treatment period + follow-up period

All previous and concomitant medication use will be listed on a single listing.

Previous medication is defined as medication with a recorded stop date before the date of the first dose of study treatment.

Concomitant medication during the 12-week treatment period is defined as medication with either a recorded medication start date falling:

- within the 12-week treatment period, or
- prior to the first day of study medication but continuing or stopping after at least 1 day on study medication

This means that concomitant medications for the 12-week treatment period will be any medication taken for at least 1 day during the 12-week treatment period.

Similarly, concomitant medications for the follow-up period will be any medication taken for at least 1 day during the follow-up period.

Anti-hyperglycemic medication taken for any reason as well as taken as rescue for severe, persistent hyperglycemia will be summarized for mITT and will also be listed. Metformin dose at baseline will be summarized, as will proportion of patients who adjusted their metformin dose during the trial.

6.8. Protocol Deviations

Important protocol deviations will be listed for all randomized patients and summarized by treatment group. A list of important protocol deviation criteria for patients from the trial issues management plan is given in [Appendix 2](#). Patients meeting criteria for important protocol deviations will be identified either by statistical programming or based off study monitoring that is maintained by the study clinical trial manager (CTM). The final list of important protocol deviations will be reviewed and documented in the Important Protocol Deviations document by the study team prior to the primary outcome DBL.

6.9. Efficacy Analyses

All statistical models will include all treatment groups, including LY3298176 and placebo.

All tests of treatment effects will be conducted at a 2-sided alpha level of 0.05 and/or 2-sided 95% CI. No adjustments for multiplicity will be performed.

6.9.1. Primary Outcome and Methodology

The primary outcome is the difference in HbA1c change from baseline between treatment groups at the end of the treatment period of 12 weeks. The primary analysis model will be a MMRM for HbA1c change from baseline to 12 weeks described in Section 6.1.1. The treatment p-value will be used as evidence of difference between active drug and placebo, whereas the comparison of LS means versus placebo (unadjusted for multiple comparisons) will provide magnitude and significance of this difference.

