4.1. Primary Objectives

The primary objective of this study is to demonstrate that at least one LY3298176 titration scheme is superior to placebo in HbA1c reduction at 3 months in patients with T2DM inadequately controlled with diet and exercise alone, or treated with a stable dose of metformin.

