6.9.1.1. Supporting Analyses of Primary Outcome

An MMRM analysis on the FAS will be performed for the primary parameter.

An ANCOVA model will be used on the last observation carried forward (LOCF) endpoint of HbA1c with fixed effects of metformin use, baseline BMI category, treatment, and baseline HbA1c as a covariate. Within the framework of this ANCOVA model, point estimates and 95% CIs for the mean change from baseline within each treatment group as well as for the difference in mean change from baseline between each investigative treatment group and placebo will be calculated. This analysis will be performed on FAS in addition to the EAS.

Table 6.3 describes the analyses to meet the primary objective, all performed on the HbA1c change from baseline values, including the above sensitivity analyses. The descriptive statistics will also be performed on the HbA1c measurements at each visit.

Table 6.3. Summary of Analyses for Primary Endpoint

Analysis Type	LOCF or Observed Values	Analysis Dataset ^a
MMRM ^b	Observed	EAS
MMRM	Observed	FAS
ANCOVA	LOCF	EAS
ANCOVA	LOCF	FAS

Abbreviations: ANCOVA = analysis of covariance; EAS = efficacy analysis set; FAS = full analysis set; LOCF = last observation carried forward; MMRM = mixed model repeated measures.

^a Refer to Table 6.2.

^b Primary analysis.

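### Does the undefined treatment p-value in SAP 6.9.1 leave the primary HbA1c test open?

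*SAP*

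**What the plan says.** The primary objective (SAP 4.1) is "to demonstrate that at least one LY3298176 titration scheme is superior to placebo in HbA1c reduction at 3 months". SAP 6.9.1 defines the primary outcome as the "difference in HbA1c change from baseline between treatment groups at the end of the treatment period of 12 weeks". It then says that "The treatment p-value will be used as evidence of difference between active drug and placebo". The second half of that sentence adds that the comparisons of LS means with placebo, not adjusted for multiplicity, supply both the size and the significance of the difference. Protocol 10.3.3.1 has the same two-part sentence.

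The model (SAP 6.1.1) contains treatment group, strata, "visit, and treatment-by-visit interaction as fixed effects". On output, the same section says: "The MMRM model will present least squares (LS) mean estimates for each scheduled week by treatment group". On p-values for group comparisons, it says: "T-statistics corresponding to the Type III sums of squares for the differences in the LS means will be used to obtain p-values".

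SAP 6.9.1.1 states that "Table 6.3 describes the analyses to meet the primary objective", and that table marks the MMRM on the efficacy analysis set as primary. SAP 6.9 adds: "All tests of treatment effects will be conducted at a 2-sided alpha level of 0.05". It also says that there is no multiplicity adjustment.

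**The concern.** The sentence in 6.9.1 contrasts a single treatment p-value with the comparisons against placebo, so a literal reader may take the first item to be the overall test of treatment. With three schemes and placebo in the model, that test has 3 degrees of freedom and no direction. It can be significant when no scheme beats placebo, and non-significant when one does.

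Because the model also has a treatment-by-visit term, a bare treatment effect could even be an average over Weeks 4, 8 and 12. In Protocol Table GPGF.3 the 12 mg or 15 mg dose begins at dose 9, on the day of the Week 8 visit. Two of the three visits would then precede any effect of the top dose.

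At stake is whether the rule that settles the primary objective is open to choice once results are known.

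**Working it through.** **Inputs.** From SAP 5.3 and Table 5.1 (the same in Protocol 10.1): 20 completers per arm, SD 1.1, mean changes −0.2 (placebo), −1.4, −1.5 and −1.5. From SAP 6.9: two-sided 0.05, unadjusted. Residual degrees of freedom: 4 × 20 − 4 = 76. Steps 1 to 3 treat Week 12 as a single-visit comparison with a common SD and no covariates.

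**1. The plan's own figure.** Standard error of a difference = 1.1 × √(2/20) = 0.348.
- 12 mg: 1.2/0.348 = 3.45; power = Φ(3.45 − 1.96) = 93.2%.
- 15 mg: 1.3/0.348 = 3.74; power = Φ(3.74 − 1.96) = 96.2%.

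With the noncentral t on 76 df these become 92.6% and 95.8%. On dropout, 92 × 0.87 = 80.04, or 20 per arm. The stated power of at least 90% is reproduced by the pairwise contrasts.

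**2. Overall test at Week 12.** The grand mean is −4.6/4 = −1.15. The squared deviations are 0.9025 + 0.0625 + 0.1225 + 0.1225 = 1.21. The noncentrality is λ = 20 × 1.21/1.1² = 20. The noncentral F with 3 and 76 df gives power of 96.8%. This also exceeds 90%, so the sample-size statement does not tell the two readings apart.

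**3. How often the two rules disagree.** Simulation of 400,000 trials per row. Superior means a Week 12 contrast significant at two-sided 0.05 in favour of LY3298176. The last two rows are assumed patterns that the documents do not give.

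| True effects | Overall test significant | At least one scheme superior | Both | Superior, overall not significant | Overall significant, none superior |
|---|---|---|---|---|---|
| Table 5.1 | 96.8% | 99.5% | 96.8% | 2.7% | 0.0% |
| No scheme works | 5.0% | 6.2% | 2.1% | 4.1% | 2.9% |
| All three better by 0.6 | 37.8% | 64.5% | 37.5% | 26.9% | 0.2% |
| One scheme worse by 1.2, others equal to placebo | 94.8% | 4.5% | 4.5% | 0.0% | 90.3% |

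**4. Averaging over visits.** The documents give no onset profile and no within-patient correlation, so any figure here is an assumption. Take 30–50% of the Week 12 effect at Week 4, 70–85% at Week 8, SD 1.1 at each visit and correlation 0.5–0.9. A difference of 1.2 then averages between 1.2 × (0.3 + 0.7 + 1)/3 = 0.80 and 1.2 × (0.5 + 0.85 + 1)/3 = 0.94, and 3-df power is 71–95%. A wider set (20–40% and 60–80% of the effect, correlation 0.5–0.85, SD 1.1 throughout or 0.7/0.9/1.1) gives 63–99%.

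**5. Which reading the text supports.** The outcome sentence just before the disputed one is fixed at 12 weeks, and nothing in either document describes averaging over visits, so step 4 illustrates a reading the plan does not invite. The p-values that SAP 6.1.1 specifies for group comparisons are t-statistics on LS-mean differences, next to LS means for each week. No F-test is named for this model. The disputed sentence concerns active drug against placebo, and its second clause gives significance to the placebo comparisons. The Week 12 contrasts are therefore produced and reported on any reading.

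**The case for a change.** The best case for a change is this. The disputed sentence is the only place in 6.9.1 that says what counts as evidence. It offers two candidates and no rule for choosing between them. Nor does it say that one significant contrast is enough. After unblinding, the analyst could pick whichever is favourable, and one added sentence would prevent that. The third row of the table shows that the rules can part company when effects are weaker than planned.

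Some of this stands. The treatment p-value is undefined, and with differences of 0.6 the two rules would disagree in about a quarter of trials. The rest is weaker than it looks.

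- **Room to choose.** The contrasts appear in the report whatever the overall test shows. A significant overall test with no superior scheme (2.9% of trials when nothing works, or the fourth row) would be exposed by comparisons planned in the same sentence. The objective itself says that at least one scheme suffices.
- **What an added sentence would decide.** Calling the overall test descriptive accepts a 6.2% chance of at least one false superiority finding when no scheme works. Requiring it to be significant first cuts that to about 2% and lowers power for at least one superior scheme from 99.5% to 96.8%. Either is defensible, so choosing one is a design preference.
- **The protocol's alpha.** At the one-sided 0.1 in Protocol 10.3.1 the 6.2% would be 21.7%. However, SAP 6.1 replaces that level and says openly that it differs from the protocol.

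**Conclusion.** The concern is a gap in wording that the rest of the plan fills. Neither document defines the treatment p-value or states a success rule. Even so, the 12-week outcome, the weekly LS means, the t-based p-values and the primary MMRM marked in Table 6.3 lead to the Week 12 comparison of each scheme with placebo at two-sided 0.05, which is the test the objective calls for.

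On documented inputs (20 per arm, SD 1.1, Table 5.1 effects) the alternative reading costs little: 96.8% against 99.5% power, with a superior contrast but a non-significant overall test in 2.7% of trials. The contrasts keep the stated power of at least 90%. Larger disagreements need effects well below those planned, or visit averaging that the 12-week outcome does not support and for which the documents give no inputs. Making the overall test descriptive or a precondition trades false superiority of 6.2% or about 2% against that small power difference. No change to the plan follows.
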